2.1.4 Safety endpoints

To address the secondary objective of evaluating the safety of insulin glargine 300 IU/mL in comparison to insulin degludec 100 IU/mL, the following endpoints will be observed

- Number of patients with adverse events (see Section 8.3 of the protocol).
- Number of patients with at least one hypoglycemic event from baseline to Week 12.
- Number of hypoglycemic events per participant-year from baseline to Week 12.

The safety analysis will be based on the reported adverse events (AEs) and other safety information, such as vital signs. The specific safety parameter of interest for insulin treatment is hypoglycemia.

Observation period

For all safety data, the observation period will be divided as follows:

- The pre-treatment phase is defined as the time from when the patients sign the informed consent to first injection of IMP (excluded).
- The on-treatment phase is defined as the time from the first injection of IMP (included) up to 2 days after the last injection of IMP.
- The post-treatment phase is defined as the time after the on-treatment phase until the end of the study (Follow up Visit).

On-study observation period is defined as the time from start of treatment until the end of the study (defined as last protocol planned visit or the resolution/stabilization of all serious adverse events (SAEs) and AEs of specific interest (AESI) as defined in the protocol).

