2.1.4.6 Hypoglycemia events

Hypoglycemia events will be evaluated during pre-treatment and on-treatment period (see Section 2.1.4).

All reported hypoglycemia events will be classified according to American Diabetes Association (ADA) classification as follows:

- Severe hypoglycemia: an event that 'Required Assistance Because Subject Was Not Capable of Helping Self'.
- **Documented symptomatic hypoglycemia**: an event during which typical symptoms are accompanied by a measured plasma glucose concentration less than 3.9 mmol/L (<70 mg/dL).
- Asymptomatic hypoglycemia: an event with no symptoms of hypoglycemia but a documented measured plasma glucose concentration less than 3.9 mmol/L (<70 mg/dL).

In addition, the following events will be also considered:

- Documented symptomatic hypoglycemia with measured plasma glucose concentration less than 3.0 mmol/L (<54 mg/dL).
- Asymptomatic hypoglycemia with measured plasma glucose concentration less than 3.0 mmol/L (<54 mg/dL).

- Hypoglycemia (symptomatic or asymptomatic) documented by a measured plasma glucose concentration less than 3.9 mmol/L (<70 mg/dL).
- Hypoglycemia (symptomatic or asymptomatic) documented by a measured plasma glucose concentration of <3.9 mmol/L (< 70 mg/dL) and \geq 3.0 mmol/L (\geq 54 mg/dL).
- Hypoglycemia (symptomatic or asymptomatic) documented by a measured plasma glucose concentration less than 3.0 mmol/L (<54 mg/dL).
- Severe and/or symptomatic hypoglycemia documented by plasma glucose concentration less than 3.9 mmol/L (<70 mg/dL).
- Severe and/or symptomatic hypoglycemia documented by plasma glucose concentration less than 3.0 mmol/L (<54 mg/dL).

In addition to anytime of the day (00:00 to 23:59), hypoglycemia events will be evaluated at the following time periods:

- Nocturnal hypoglycemia: any hypoglycemic event that occurs between 00:00 and 05:59.
- Diurnal hypoglycemia: any hypoglycemic event that occurs between 06:00 and 23:59.

Note: CGM values will not be considered for identifying hypoglycemia.

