2.4.3.1 Extent of investigational medicinal product exposure

The extent of IMP exposure will be assessed by the duration of IMP exposure over the study period.

The duration of treatment exposure will be the total number of days of administration of the open-label IMP, regardless of unplanned intermittent discontinuations (see Section 2.5.3 for calculation in case of missing or incomplete data). The duration of IMP exposure will be calculated as:

• (date of the last open-label IMP injection – date of the first open-label IMP injection) + 1.

Duration of IMP exposure will be summarized descriptively as a quantitative variable (number, mean, SD, median, minimum, and maximum). In addition, duration of treatment exposure will also be summarized categorically by numbers and percentages for each of the following categories and cumulatively according to these categories 1 to 21 days, 22 to 42 days, 43 to 63 days, 64 to 84 days and >84 days.

Additionally, the cumulative duration of treatment exposure will be provided, defined as the sum of the duration of treatment exposure for all patients, and will be expressed in patient years.

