2.4.5.1 Analyses of hypoglycemia events

Incidence of patients with at least one hypoglycemia event

A frequency table showing the number and % of patients experiencing at least one hypoglycemic event will be presented for any hypoglycemia and for each type of hypoglycemia (see

Section 2.1.4.6), overall and according to time of occurrence (nocturnal [ie, 00:00 to 05:59], for any time of day and daytime [ie, 06:00 to 23:59] during the on-treatment period.

The Odds Ratio and its corresponding 95% CI for the Toujeo arm over the Tresiba arm for each hypoglycemic event (nocturnal and any time of the day) during the on treatment period will be estimated by a logistic regression model adjusted on randomization strata of screening HbA1c.

Number and rate of hypoglycemia event

The number and rate of hypoglycemic events (in patient-year of exposure) will be determined for any hypoglycemia and for each type of hypoglycemic event, overall and according to time of occurrence (nocturnal [ie, 00:00 to 05:59], any time of the day) during the on treatment period and in the pre-treatment period.

For each type of hypoglycemic event during the on treatment period, the rate ratio, and its corresponding 95% CI, for the Toujeo arm over the Tresiba arm will be estimated using an over-dispersed Poisson regression model adjusted on randomization strata of screening HbA1c.

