2.5.3 Missing data

For categorical variables, patients with missing data are not included in calculations of percentages unless otherwise specified. When relevant, the number of patients with missing data is presented.

Handling of computation of treatment duration if investigational medicinal product end of treatment date is missing

For the calculation of the treatment duration, the date of the last dose of IMP is equal to the date of last administration reported on the Completion of End of Study/Follow-up case report form page. If this date is missing, the exposure duration should be left as missing.

Handling of medication missing/partial dates

No imputation of medication start/end dates or times will be performed. If a medication date or time is missing or partially missing and it cannot be determined whether it was taken prior or concomitantly, it will be considered a prior, concomitant, and post-treatment medication.

Handling of adverse events with missing or partial date/time of onset

Missing or partial adverse event onset dates and times will be imputed so that if the partial adverse event onset date/time information does not indicate that the adverse event started prior to treatment or after the treatment-emergent adverse event period, the adverse event will be classified as treatment-emergent. No imputation of adverse event end dates/times will be performed. These data imputations are for categorization purpose only and will not be used in listings. No imputation is planned for the date/time of adverse event resolution.

Handling of adverse events when date and time of first investigational medicinal product administration is missing

When the date and time of the first IMP administration is missing, all adverse events that occurred on or after the day of randomization should be considered as treatment-emergent adverse events. The exposure duration should be kept as missing.

Handling of missing assessment of relationship of adverse events to investigational medicinal product

If the assessment of the relationship to IMP is missing, then the relationship to IMP has to be assumed and the adverse event considered as such in the frequency tables of possibly related adverse events, but no imputation should be done at the data level.

Handling of missing responses of DTSQc and DTSQs

The total treatment satisfaction score is the sum of items 1, 4, 5, 6, 7 and 8.

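### On-treatment hypoglycemia events are counted to 2 days after the last injection, but the only exposure time the SAP defines ends at the last injection, so on-treatment rates per patient-year come out slightly high

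*SAP*

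**What the plan says.** **Event window.** SAP 2.1.4 defines the on-treatment phase as running "from the first injection of IMP (included) up to 2 days after the last injection of IMP"; Protocol 9.4.2 sets the same limits. SAP 2.1.4.6 states: "Hypoglycemia events will be evaluated during pre-treatment and on-treatment period", and refers back to 2.1.4.

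**Rate.** SAP 2.4.5.1 states: "The number and rate of hypoglycemic events (in patient-year of exposure) will be determined". It plans this for night-time and "any time of the day) during the on treatment period and in the pre-treatment period". Rate ratios come from an over-dispersed Poisson model adjusted for HbA1c stratum. No formula for the person-time and no offset is given.

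**Exposure.** The one definition is in SAP 2.4.3.1: (last injection date minus "date of the first open-label IMP injection) + 1". The cumulative figure there is "defined as the sum of the duration of treatment exposure for all patients, and will be expressed in patient years". The 2 extra days are not added.

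**Missing dates.** SAP 2.5.3 takes the last-dose date from the end-of-study form and adds: "If this date is missing, the exposure duration should be left as missing". It also leaves exposure missing when the first-dose date and time are missing.

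**The concern.** A rate needs events and time at risk from the same window. Here the event window extends past the last injection, while the only defined exposure stops there. Events in the final stretch would enter the numerator with no matching time in the denominator. Those days are observed: the Protocol's schedule of activities records hypoglycemia throughout the study and places the follow-up visit 2 to 4 days after the last dose.

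The number of hypoglycemic events per participant-year is a stated secondary safety endpoint (Protocol Table 1, SAP 2.1.4), and SAP 2.1.4 singles out hypoglycemia as the safety parameter of interest for insulin. What is at stake is the accuracy of the absolute rates in the report, together with two gaps beside it: the pre-treatment rates have no usable denominator, and patients without a last-dose date have no stated handling.

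**Working it through.** The documents give no hypoglycemia rate, event count or total exposure, so there is no planned figure to reproduce. The check compares two denominators for the same events.

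**Inputs**
- Planned treatment: 12 weeks, or 84 days (Protocol synopsis).
- Planned patients: 169 per arm (SAP 1.3).
- Exposure: T = last injection date − first injection date + 1 (SAP 2.4.3.1).
- Event window: to 2 days after the last injection (SAP 2.1.4). As calendar days it has length T + 2. As 48 hours from the last injection it has length T + 1, because T already counts the whole day of that injection. The SAP does not say which is meant.
- Assumptions, not in the documents: a year of 365.25 days for person-time, and the discontinuation patterns below.

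**Formula.** The events are the same either way, so reported rate ÷ window-matched rate = (T + 2)/T, or (T + 1)/T on the 48-hour reading. This ratio needs no assumption about the daily event rate.

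**One completer, T = 84**
- Calendar days: 86/84 = 1.024, or +2.4%.
- 48 hours: 85/84 = 1.012, or +1.2%.
- A matched rate of 10 per patient-year would be reported as 10 × 86/84 = 10.24, or 10 × 85/84 = 10.12.

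**One arm of 169 completers**
- Exposure as defined: 169 × 84/365.25 = 38.87 patient-years.
- Matched: 169 × 86/365.25 = 39.79 patient-years.

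**Arm with early stopping (calendar days).** If a fraction d stops at day t, mean exposure is E = (1 − d) × 84 + d × t, and the factor is (E + 2)/E.

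| d | t | E (days) | Factor |
|---|---|---|---|
| 0 | – | 84.00 | 1.0238 |
| 5% | 42 | 81.90 | 1.0244 |
| 10% | 42 | 79.80 | 1.0251 |
| 22% | 42 | 74.76 | 1.0268 |
| 22% | 14 | 68.60 | 1.0292 |

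The range per arm is +2.4% to +2.9%. On the 48-hour reading each excess halves, giving +1.2% to +1.5% (69.60/68.60 = 1.0146).

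**Rate ratio (crude)**
- 5% versus 10% stopping at day 42: ratio of the two arm factors = 1.0006.
- Extreme case, 0% versus 22% stopping at day 14: 1.0292/1.0238 = 1.005.

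**Pre-treatment rates.** There are no study injections before the first one, so the 2.4.3.1 formula has no value in that period. The mismatch above does not apply to these rates; their denominator is simply not defined.

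**The case against.** The strongest reply is that SAP 2.4.3.1 serves its own purpose, the extent of exposure, and is correct for it. SAP 2.4.5.1 does not refer to it. The same sentence plans pre-treatment rates, where that formula cannot apply, so exposure in 2.4.5.1 cannot mean the 2.4.3.1 quantity throughout. This stands to the extent that the link is inferred, and one cannot say that the SAP prescribes the mismatched denominator. But 2.4.3.1 is the only definition a programmer will find, and it is already summed into patient-years. If something else was meant, the denominator of a stated secondary endpoint is undefined and the sentence is still needed.

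A second reply is that treatment after the last dose is at the treating physician's discretion (Protocol 6.7), so the event rate may change in those days. The comparison with matched person-time is unaffected, because both rates use the same events. It does matter if the reported rate is read as the on-drug rate. If the post-dose rate is k times the on-drug rate, the excess for a completer is 2k/84: 0% for k = 0, 1.2% for k = 0.5, 4.8% for k = 2.

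Third, a reader might infer that missing last-dose dates also inflate the rates. The documents do not support this. SAP 2.5.3 leaves the exposure missing but does not say that the events are kept. A crude rate could keep the events without any time, whereas a Poisson model with a missing offset would drop the patient's events and time together. What stands is the ambiguity: crude rates and rate ratios could rest on different patients.

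**Conclusion.** The mismatch is real on the natural reading of the SAP, and it is small. On-treatment hypoglycemia rates above zero are overstated against matched person-time by about 1.2% to 2.4% for a completer and by at most about 2.9% per arm. The upper figure rests on assumed discontinuation of 22% at day 14 and on reading 2 days as calendar days.

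Three stronger readings are tempting and do not hold:
- That every rate per patient-year is overstated. Pre-treatment rates are also planned and are not inflated this way.
- That the error is large. For single patients the factor reaches 23/21 (+9.5%) for a stop at day 21 and 9/7 (+29%) at day 7, but the SAP reports rates by arm, where such patients are averaged with completers.
- That the treatment comparison is biased. The rate ratio shifts by a factor of about 1.0006 with modestly different discontinuation, and about 1.005 in an extreme assumed case.

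Proportions with an event and odds ratios use no exposure time. Hypoglycemia lies outside the testing hierarchy (SAP 2.4.4.3), and the safety analysis is essentially descriptive (SAP 2.4.5). No trial conclusion depends on this point. It is worth correcting because a reported endpoint comes out slightly wrong and the correction is nearly free.

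**What to change.** **SAP 2.4.5.1**
- Define the denominator of on-treatment hypoglycemia rates, and the log offset of the Poisson model, as time in the on-treatment phase: first injection to last injection + 2 days, truncated at the end of study observation.
- State whether 2 days means calendar days or 48 hours.
- Give pre-treatment rates their own denominator: time from consent to first injection.

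**SAP 2.5.3**
- For hypoglycemia rates, when the last-dose date is missing, use the last documented dosing date. Protocol 8.1.5 provides sources: the daily diary, the weekly calls, and the eCRF entries for the last 3 days before permanent discontinuation.
- Do not use the last contact date. Patients who stop study insulin are asked to stay in the study to Week 12 (Protocol 7.1.1), so a patient who stopped at day 7 and was followed to day 84 could gain up to 84 − 7 = 77 days off treatment, far more than the 2 days at issue.
- State that a patient's events and time are kept or excluded together, in both the crude rates and the model.

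The cost is a few sentences and no new data. The definition of extent of exposure in 2.4.3.1 can stay as it is. The one downside is that reported on-treatment rates become slightly lower.

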2.4.3.2 Daily insulin doses

Daily insulin dose will be summarized descriptively (number, mean, SD, median, Q1, Q3, minimum, and maximum) at each visit (baseline, and post baseline: Week 8 and Week 12).

Basal insulin daily dose (U and U/kg) at baseline is defined as the actual starting IMP dose of basal insulin as reported by the Investigator into the e-CRF (first IMP intake).

Mealtime insulin (ie, rapid acting insulin analog) daily dose (U and U/kg) at baseline is defined as the actual mealtime total daily dose in run-in (see Section 2.1.1).

At each postbaseline visit, the daily basal, mealtime, and total (basal plus mealtime) insulin doses (U and U/kg) will be calculated as the mean of total daily insulin doses (as reported in the CRF) collected in the week before the corresponding visit.

The change from baseline daily doses variable at Week 8 and Week 12 will also be summarized descriptively.

2.4.3.3 Compliance

A given administration will be considered noncompliant if the patient did not take the IMP as required by the protocol, meaning one injection per day. No imputation will be made for patients with missing or incomplete data.

The percentage of compliance for a patient will be defined as the number of days with at least one administration divided by the duration of IMP exposure.

Treatment compliance will be summarized descriptively as quantitative variables (number, mean, SD, median, minimum, and maximum) by treatment group for the safety population. In addition, numbers and percentages of patients whose compliance is <80% will be summarized by treatment group.

2.4.4 Analyses of efficacy endpoints

For each patient, the number of days with useable CGM data within the analysis time window (see Section 2.5.4) will be derived in the following categories: < 10 days, 10 days, 11 days, 12 days, 13 days, 14 days, ≥ 14 days at baseline and at Week 12. The categories could be updated based on real data.

2.4.4.1 Analysis of primary efficacy endpoint(s)

2.4.4.1.1 Primary efficacy analysis

The primary efficacy endpoint is the percent time in glucose range is defined as the proportion of CGM readings falling into the range of \geq 70 to \leq 180 mg/dL [\geq 3.9 to \leq 10 mmol/L] at the Week 12 evaluation.

The primary efficacy endpoint will be analyzed using available data from the 12-week randomized period in ITT population via an analysis of covariance (ANCOVA) including the fixed categorical effects of treatment group (Toujeo versus Tresiba), randomization stratum of screening HbA1c (<8.0% versus \geq 8.0%), as well as, the continuous fixed covariate of baseline percent time in range value.

Multiple imputation (MI) assuming missing at random (MAR) will be used to replace missing data of percent time in glucose range at Week 12 and at baseline. The MAR assumption means that the missingness depends only on observed variables and not on the data that would have been observed (in the present case, the percent time in glucose range that would have been observed).

Moreover, the imputation procedure will also depend on the observed pattern of missingness:

- A) Monotone Pattern: Patients with missing baseline CGM and missing Week 12 CGM, or patients with baseline CGM but without a Week 12 value.
- B) Non-Monotone Pattern: Patients with missing baseline CGM but with a Week 12 CGM. Baseline CGM evaluable being used as a criterion to allow the randomization, this pattern is not expected to be represented in the study.

In order to explore missing data patterns for the primary efficacy analysis, number and percentage of patients in each of the following categories will be presented by treatment group.

- Pattern 1: patients with missing baseline CGM and missing Week 12 CGM,
- Pattern 2: patients with baseline CGM but missing Week 12 CGM,
- Pattern 3: patients with missing baseline CGM but with Week 12 CGM,
- Pattern 4: patients with baseline CGM and Week 12 CGM

Once missing data pattern will be assessed, the three-step programming process described in Section 2.5.3 will provide baseline-adjusted least-squares means estimates at Week 12 for both treatment groups, as well as, the differences of these estimates, with their corresponding standard errors (SEs), 95% CI, and one-sided P-values (H0: m1 - $0.9 \times m0 \le 0$, with m1 = true mean of Toujeo and m0 = true mean of Tresiba).

Toujeo would be considered non-inferior to Tresiba if the lower limit of the 95% CI for the adjusted difference estimate of m1-0.9*m0 at Week 12 is > 0 (with m1=true means of Toujeo and m0=true means of Tresiba).

01-Jul-2021 Version number: 1

In addition to the non-inferiority testing that is the primary analysis, and only if non-inferiority of Toujeo in comparison to Tresiba on the percent time in the range of 70-180 mg/dL is demonstrated and if non-inferiority of Toujeo versus Tresiba on the glucose total CV is demonstrated (see Section 2.4.4.3 for multiplicity issues), superiority of Toujeo over Tresiba on the percent time in the range of 70-180 mg/dL will be tested.

The point estimate of difference in mean of percent time in range and the corresponding 95% CI will also be estimated using the following ESTIMATE statement in PROC GLM (in Step 2, See Section 2.5.3).

ESTIMATE "TOUJEO-TRESIBA" TREAT 1 -1

and the Step 3 will be done to obtain baseline-adjusted least-squares means estimates at Week 12 for both treatment groups as well as, the differences of these estimates, with their corresponding standard errors (SEs), 95% CI. The lower bound of the two-sided 95% CI for the adjusted difference estimate of m1 - m0 at Week 12 will be compared to 0 and subjected to a superiority test (if lower limit of 95% CI is >0).

The superiority comparison is considered as a secondary analysis of the primary efficacy variable.

Assumption assessment

The studentized residuals from the 1000 ANCOVA models described in Step 2 above with imputed data will be inspected and plotted against the predicted values, all in the same graph, for a visual assessment to detect any homoscedasticity.

2.4.4.1.2 Sensitivity analyses

First sensitivity analysis: MI on the PP population

A first sensitivity analysis will be performed on the PP population (see Section 2.3.1.2) with the same multiple imputation process as for primary analysis.

Second sensitivity analysis: MI under missing not at random (MNAR) assumption on ITT population

In addition, to investigate possible violations of the MAR assumption, a second sensitivity analysis with multiple imputation in conjunction with MNAR assumption based on patient status at Week 12 will be performed for ITT population.

Under the MNAR assumption, patients with study treatment discontinuation without any CGM done at Week 12 and patients with missing CGM endpoints at Week 12 due to other reasons (ie, non-evaluable CGM) will be imputed differently.

This MI process for the missing data can be carried out in two parts:

- For patients who prematurely discontinue the study treatment, as it is not expected to have enough patient who discontinued with CGM at Week 12 done, hypothesis of return to baseline will be used. The imputation for Week 12 will be from the following model ~ N (BASE, SD) (BASE is the baseline value for the patient, SD estimated for all patients at baseline)
- 2. For patients who did not prematurely discontinue the study treatment, the multiple imputation method described as the primary efficacy analysis under MAR assumption will be used.

Missing values will be imputed 1,000 times. For each imputation, the two completed datasets from the two parts detailed above will be combined into one single completed dataset. Each completed dataset will then be analyzed though an ANCOVA model which will include fixed categorical effects of treatment group, randomization stratum screening HbA1c value [<8.0% versus $\geq 8.0\%$], as well as fixed continuous fixed covariate of baseline percent time in range value. The final results will be obtained by combining the least squares (LS Means) means and LS mean differences from these 1,000 analyses, using Rubin's formula.

Third sensitivity analysis: MI on Population without trial impact (disruption) due to COVID-19

A third sensitivity analysis will be performed on Population without trial impact (disruption) due to COVID-19 (see Section 2.3.1.3) with the same multiple imputation process as for primary analysis.

